10.2 Other Endpoints

a. HBV reactivation is defined as one of the following:

- ≥ 2 log (100-fold) increase in HBV DNA compared to baseline in patients with detectable HBV DNA at baseline, or
- HBV DNA ≥ 3 log (1,000) IU/mL in a patient with previously undetectable HBV DNA, or
- HBV DNA ≥ 4 log (10,000) IU/mL if baseline HBV DNA not available, or
- HBsAg seroreversion (HBsAg- to HBsAg+) in a patient previously HBsAg-.

b. Hepatitis flare: Hepatitis flare is defined as ALT $> 3 \times$ baseline and >100 U/L.

c. Upon indication: On Arms 2 and 3, anti-HBV therapy is initiated only when HBV reactivation occurs (see [Section 10.2a](#)). Once started, anti-HBV therapy continues for a minimum of 6 months after discontinuation of all anti-cancer therapy or for up to 24 months after registration, whichever comes first (see [Section 7.6](#)).

d. Cancer therapy interruption is defined as dose reduction, treatment delay, or termination of anti-cancer therapy due to hepatic-related reasons other than disease progression in the liver.

e. Death due to any cause measured from date of randomization to date of death.

11.0 STATISTICAL CONSIDERATIONS

11.1 Primary Endpoint

The following design pertains to each of the different study cohorts (chronic HBV [Cohort 1] and past HBV [Cohort 2]).

The primary endpoint for the clinical study is the time until adverse liver outcome. Patients will be assessed every 4 weeks (+/- 2 weeks) for the first 24 weeks, then every 8 weeks until 24 months. The study will recruit patients with multiple different cancer types, but predominantly lung, breast, colon, prostate, gynecological, and head and neck cancers. Since patient prognosis is sufficiently poor to be receiving anti-cancer therapy, dropout due to non-liver related death will be a significant factor in the design. One-year overall survival is anticipated to be 80% for the combined cohort. Therefore, non-liver related death represents a competing risk in the detection of adverse liver outcomes, which is accounted for in the study design. Both time to first evidence of adverse liver event and non-liver related death are assumed to exhibit exponential decline.

The rate of adverse liver outcomes in this population is not well characterized, as most studies in the literature only report on rates of HBV reactivation or hepatitis flares. For design purposes, the best estimate of the researchers is that 10% of both chronic (Cohort 1) and past (Cohort 2) HBV patients will experience an adverse liver outcome within one

The primary analysis for each randomized experiment will be based on central, blinded review of adverse liver events among all randomized, eligible patients. A secondary examination in all randomized patients irrespective of their eligibility status will also be conducted under a fully intent-to-treat approach. To account for the potential for liver events to vary by cancer stage over and above what is reflected by the stratification variable (planned treatment type), in a secondary analysis, the investigators will adjust for cancer stage (adjuvant vs. advanced disease) as a covariate in the multivariable Cox regression model.

11.2 Secondary Endpoints

The main secondary objective for each randomized cohort is to determine the incidence of HBV reactivation among patients with solid malignancies and chronic or past HBV infection during or after completion of anti-cancer therapy. Based on preliminary data, it is anticipated that 20% of patients will experience HBV reactivation on the standard arm of each of the randomized trials. Estimates of HBV reactivation at one year will be derived using cumulative incidence to account for competing risks. Under this scenario, a sample size of n=222 patients for each randomized study will allow the investigators to estimate the confidence interval to within $\pm 6\%$ (based on the upper bound of the 95% confidence

interval using an exact binomial in patients with complete follow-up), if the assumed incidence is at least 20%. Thus, this sample size will allow the confidence interval to be estimated to within $\pm 31.1\%$ of the assumed incidence (the “relative accuracy”, defined as: (95% CI upper bound – p)/p], where p is the assumed incidence). This estimate is conservative as it is based on the assumption of no information from the 10% of patients estimated to drop out.

The investigators will also compare HBV reactivation rates by arm within each randomized trial. Based on a two-sample survival design accounting for the competing risk of death (~20% deaths at 1 year [hazard rate of 0.223]), and a one-sided alpha=0.05 test, then n=222 patients (111 per arm) will give 81% power to detect a hazard ratio for HBV reactivation for experimental to standard arms of 0.47, representing a 53% reduction in the hazard risk of HBV reactivation in the first year (from a hazard=0.223 down to hazard=0.105), or an absolute reduction of 50% (from 20% down to 10%). Multivariable Cox regression will compare the effect of intervention assignment, adjusting for the stratification factors specified in the main clinical study.

The investigators will also determine the cumulative incidence of the combined endpoint of adverse liver events plus HBV reactivation, as well as the cumulative incidence of hepatitis flare, by arm within each randomized trial and compare it between the arms in similar fashion.

The accrual for this study is expected to come primarily from NCORP community sites. The estimated rate of past HBV infection in the cancer population is 4.6% based on studies by Ioannou and Roberts. (49,50) A slightly higher rate of 5% is assumed based on the expected enrollment distribution by race for this study using data from [S1204](#). To enroll 222 eligible patients to the past HBV cohort, $222/0.05 = 4440$ patients would need to be screened. Although it is typically estimated that one in 20 patients agree to enroll to a clinical trial, within SWOG sites this rate was found to be higher (14%) in a prospective SWOG barriers study. (51) Therefore, it is estimated that 1 in 7 patients identified as having past HBV infection will enroll to this trial, so $4440*7 = 31,080$ patients in total will need to be screened. If 60 sites participate equally, each site would need to screen 18 patients/month to complete the study in 2.5 years.

The estimated rate of chronic HBV infection in the cancer population is 0.3% based on studies by Ioannou and Roberts. (52,53) Again, a higher rate, of 0.5% is assumed, based on the expected enrollment distribution by race for this study using data from [S1204](#). To enroll 222 eligible patients to the chronic HBV cohort, using the same approach as above, it is estimated that 310,800 patients will need to be screened. Each participating site would need to screen 110 patients/month to complete this portion of the study in 4.0 years.

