Only the patients randomized to the standard arm of each randomized study (chronic vs. past HBV infection) will be the potential participants for this aim. A case-control analysis, using a ratio of cases to controls of 1:1, will be conducted to explore baseline and changes of overall immune status and HBV-specific immune response factors that differ between patients with vs. without HBV reactivation. Based on expected rates of HBV reactivation for patients with chronic and past HBV infection (20%), we estimate that 22 patients with chronic and 22 patients with past HBV infection (n=44 total cases) will develop HBV reactivation. Under this scenario, we will also examine a matched set of 44 control patients. Matching will occur based on age and randomized study type (chronic vs. past HBV infection). Power is low in this setting and therefore this aim is considered exploratory, with any positive findings requiring validation in future studies. For a given binary predictor (i.e. immune status, group 1 = high vs. group 2 = low), 88 total patients (44 cases and 44 controls) is sufficient to detect an absolute difference of 26% in HBV reactivation rates (i.e. 7% for group 1 and 33% for group 2), assuming the overall rate of HBV reactivation is 20%, using a 2-arm binomial alpha=.05 test with 80% power. In addition, changes in overall immune status and HBV-specific immune responses after onset of cytotoxic chemotherapy or immunotherapy will be described for the cases and controls using descriptive statistics (means, standard deviations). To avoid incorrect inference induced by the potentially endogenous relationship between HBV reactivation and immune response, landmark analyses will be used, conditioning on patients surviving to a given assessment time without developing HBV reactivation.

The study will also assess the association of potential risk factors (including demographic, clinical, and immunologic markers) for HBV reactivation. For any potential demographic, clinical, or immunologic factor, time-to-HBV reactivation will be examined using Cox regression, adjusting for the stratification factors specified in the main clinical study. Analyses will be conducted for each randomized study (chronic vs. past HBV), each with a total sample size of n=222 patients. For instance, to identify a hazard ratio of 2.5 between patients with or without a given condition (say, status for a specified candidate marker or

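### Section 11.2's 31.1% relative accuracy for HBV reactivation assumes 20% in both arms although the section plans 20% and 10%, and the 26% difference in 18.1 is a cohort calculation, not one for 44 cases and 44 controls

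*Combined protocol and SAP*

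**What the plan says.** **Section 11.2.** The planning rate belongs to one arm: "it is anticipated that 20% of patients will experience HBV reactivation on the standard arm of each of the randomized trials". The estimand is given a time point: "Estimates of HBV reactivation at one year will be derived using cumulative incidence to account for competing risks". The precision statement then covers both arms: "a sample size of n=222 patients for each randomized study will allow the investigators to estimate the confidence interval to within" 6 points, using the upper limit of an exact binomial 95% interval in patients with complete follow-up, provided the incidence is 20% or more. Relative accuracy, defined as (upper limit − p)/p, is put at 31.1%, with the 10% who drop out contributing nothing. The next paragraph plans the arm comparison on hazards of 0.223 and 0.105, "or an absolute reduction of 50% (from 20% down to 10"%).

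**Section 18.1, statistical analysis of the translational aims.** The source population for the case-control work is restricted: "Only the patients randomized to the standard arm of each randomized study". The case count follows from the same 20%: "we estimate that 22 patients with chronic and 22 patients with past HBV infection (n=44 total cases) will develop HBV reactivation". Controls are matched 1:1. Power is then stated as follows: "88 total patients (44 cases and 44 controls) is sufficient to detect an absolute difference of 26% in HBV reactivation rates", namely 7% vs 33% with 20% overall, "using a 2-arm binomial alpha=.05 test with 80% power". The sentence does not say whether the test is one- or two-sided.

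**Matching.** Under Translational Aim 1, section 18.1 matches on age in 5-year strata, sex, type of anti-cancer therapy, and chronic or past HBV. The statistical paragraph lists only age and chronic or past HBV.

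**The concern.** In 11.2, a rate stated for the standard arm is applied to all 222 patients of a cohort, half of whom are planned to have half that rate. Section 18.1 applies the same 20% to the standard arm only: 0.20 × 111 = 22.2, the 22 cases per cohort. The incidence of reactivation is the main secondary objective, so its stated precision should follow from the section's own rates.

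In 18.1, the sentence names 44 cases and 44 controls but assumes an overall reactivation rate of 20%. A 1:1 sample has 50% cases by construction and cannot estimate reactivation rates. A difference between such rates is therefore not what the sample can detect. A reader relying on that sentence would misjudge the sensitivity of the aim, and could not select controls until the two matching lists agree.

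**Working it through.** **A. Precision in 11.2**

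Inputs from sections 11.1 and 11.2: 222 patients per cohort (111 per arm); 10% dropout; one-year reactivation 20% standard and 10% experimental; hazards 0.223 and 0.105; death hazard 0.223. The upper limit U for x events in n is the 97.5% quantile of Beta(x + 1, n − x). Relative accuracy is (U − p)/p.

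1. Plan's figure. n = 222 × 0.9 ≈ 200 and x = 0.20 × 200 = 40. U = 26.22%, so +6.2 points and 6.22/20 = 31.1%. It reproduces.
2. Whole cohort at the section's own rates. Pooled p = (20% + 10%)/2 = 15%, x = 30. U = 20.72%, so +5.7 points and 5.72/15 = 38.1%.
3. With death competing. Cumulative incidence at time t is h/(h + d) × [1 − exp(−(h + d)t)]. At one year:
   - standard arm: 0.223/0.446 × (1 − e^−0.446) = 18.0%
   - experimental arm: 0.105/0.328 × (1 − e^−0.328) = 9.0%
   - pooled 13.5%, or 27/200: U = 19.0%, +5.5 points, 41.0%.
4. At 24 months the same formula gives 29.5% and 15.4%, pooled about 22.5%, or 45/200: U = 28.9%, +6.4 points, about 29%.
5. Standard arm alone at one year, 111 × 0.9 ≈ 100 completers, 20/100: U = 29.2%, +9.2 points, 45.9%.
6. The 20%-or-more condition. At 60/200 (30%), U = 36.9%: +6.9 points, 22.9%. As incidence rises from 20%, relative accuracy improves but the absolute half-width widens.

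**B. Case-control sentence in 18.1**

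Formula, two-sided α = 0.05 and 80% power:

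m = [1.96 √(2p̄(1 − p̄)) + 0.842 √(p₁(1 − p₁) + p₂(1 − p₂))]² / (p₁ − p₂)²

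With continuity correction, n = (m/4)[1 + √(1 + 4/(m|p₁ − p₂|))]².

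1. Plan's figure. p₁ = 0.07, p₂ = 0.33: m = 36.0, n = 43.3, rounded up to 44 per group. One-sided gives 29 without and 36 with the correction. So 44 arises as a two-sided, continuity-corrected comparison of two predictor groups.
2. Cases in that comparison: 44 × 0.07 + 44 × 0.33 = 17.6 of 88. The planned sample has 44 of 88.
3. Implied odds ratio: (0.33/0.67)/(0.07/0.93) = 6.5.
4. The same scenario seen as a case-control study with equal predictor groups. Share of cases in the 33% group: 0.33/0.40 = 82.5%. Share of controls: 0.67/1.60 = 41.9%. Power for 44 vs 44, unmatched and two-sided, is about 97–98%, not 80%.
5. Detectable odds ratio for 44 vs 44, unmatched, two-sided, 80% power. Control exposure is an assumption because the documents give none.

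| Control exposure | No correction | With correction |
|---|---|---|
| 20% | 3.7 | 4.1 |
| 30% | 3.4 | 3.7 |
| 40% | 3.4 | 3.8 |
| 50% | 3.6 | 4.1 |

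6. Fewer usable cases. At 18 per 100 standard-arm completers (step A3) there would be 36 cases over the two cohorts. The range becomes 3.9–4.2 without and 4.4–5.0 with the correction.

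**The case against.** Several defences have force.

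- **The population is named.** A reader might infer that 11.2 leaves it open. It does not: the statement is for 222 patients per randomized study. The standard-arm result of 46% therefore answers a claim the plan does not make, and is only an optional addition.
- **The absolute precision is not overstated.** At 15% the margin is 5.7 points, tighter than the 6.2 behind the plan's figure. Only the ratio moves, because its denominator shrinks.
- **The figure does not require a null effect.** It is tempting to say that 31.1% holds only if the intervention does nothing. A pooled 20% also arises from, say, 27% and 13%, and the plan conditions on an incidence of at least 20%. The supportable claim is narrower: a pooled 20% at one year conflicts with the section's own 20% and 10%.
- **A later time point would meet the condition.** At 24 months the plan's hazards pool to about 22.5%, and relative accuracy is better than stated. But 11.2 names one year for this estimate, so the time point needs stating either way.
- **The case-control aim is declared exploratory, with low power acknowledged.** That stands. A reader might infer from the mismatch that the aim is weaker than claimed; at 44 and 44 the calculation shows the opposite. The odds ratios are not settled values, however. Whole blood for the cellular assays is optional (section 15.2), so usable cases may be fewer, and within-pair correlation from matching would need an assumption that the documents do not give.

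**Conclusion.** Both stated figures are arithmetically sound but attached to the wrong setting.

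In 11.2, at the section's own one-year rates, whole-cohort relative accuracy is about 38% rather than 31.1%, or about 41% if competing death lowers the pooled incidence to 13.5%. The 6 points stands. This rests on equal arms, 10% dropout giving no information, and the planned 20% and 10%.

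In 18.1, the 26-point difference is not the detectable effect of 44 cases and 44 controls. On an unmatched two-sided basis, with assumed control exposure of 20–50%, that effect is an odds ratio of about 3.4–3.7 without and 3.7–4.1 with continuity correction, against an implied 6.5. The error is conservative and the aim stays exploratory. The two matching lists do conflict.

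Severity is minor. Nothing here bears on enrolment, the primary analysis or the comparison of reactivation between arms.

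**What to change.** **Section 11.2.**
- Restate the relative accuracy as about 38% for the whole cohort at one year, at the design's pooled 15%, and keep about 6 points as the absolute figure.
- If 24 months is meant, say so and restate it at about 22.5% pooled and about 29%.
- If a standard-arm estimate is also wanted, give it separately: 20/100, about +9 points, 46%.
- Attach the 20%-or-more condition to the relative accuracy only, with whatever incidence is finally used.

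**Section 18.1.**
- Replace the 26% sentence with a detectable odds ratio for 44 cases vs 44 controls at 80% power. State that the test is two-sided, whether a continuity correction is used, and the range of control exposure. Add that fewer usable cases would raise the detectable value.
- Reconcile the matching factors given under Translational Aim 1 with those in the statistical paragraph.
- Name an analysis that respects the matching, such as conditional logistic regression.

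The cost is wording and a short recalculation. The 11.2 ratio at one year becomes less favourable and the case-control figure more favourable. Data collection does not change.

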1.2 Secondary Objectives

- a. Using time-to-event analysis, to compare the effect of anti-HBV therapy versus upon indication anti-HBV therapy on HBV reactivation, on the combined endpoint of adverse liver outcomes (liver failure or liver-related death) and HBV reactivation, and on HBV flare by arm in patients with chronic HBV infection receiving anti-cancer therapy for solid tumors.
- b. Using time-to-event analysis, to compare the effect of upon indication anti-HBV therapy versus usual care on HBV reactivation, on the combined endpoint of adverse liver outcomes (liver failure or liver-related death) and HBV reactivation, and on HBV flare by arm in patients with past HBV infection receiving anti-cancer therapy for solid tumors.

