7.3 Cohort 2: Past HBV Anti-Viral Treatment

a. Arm 3: Upon Indication Anti-Viral Therapy

The treating investigator and patient will choose the appropriate anti-viral therapy from one of the three anti-viral therapies below. Patients may initiate anti-viral therapy with a reduced dose based on creatinine clearance (see Dose Modifications, [Section 8.2](#)).

Monitor ALT at least every 4 weeks (+/- 2 weeks) as part of trial monitoring for the first 24 weeks, then every 8 weeks thereafter. If hepatitis flare occurs (see definition for hepatitis flare in [Section 10.2b](#)), then obtain HBV DNA test per usual care. Start anti-HBV therapy if HBV reactivation occurs.

Agent	Dose	Route	Start Day	Schedule
Tenofovir alafenamide (TAF)	25 mg ^A	PO ^B	As soon as possible after HBV reactivation occurs (see criteria for HBV reactivation Section 10.2a).	Daily for up to 6 months after the last dose of anti-cancer therapy or a maximum of 24 months ^C .
Tenofovir disoproxil fumarate (TDF)	300mg	PO	As soon as possible after HBV reactivation occurs (see criteria for HBV reactivation. Section 10.2a	Daily for up to 6 months after the last dose of anti-cancer therapy or Maximum of 24 months
Entecavir (ETV)	0.5mg	PO	As soon as possible after HBV reactivation occurs (see criteria for HBV reactivation. Section 10.2a	Daily for up to 6 months after the last dose of anti-cancer therapy or Maximum of 24 months.

^A In patients taking carbamazepine the TAF dose will be increased to 50 mg daily.

^B See dosage administration details in [Section 3.1d](#).

Anti-HBV therapy is initiated only when HBV reactivation. Once started, anti-HBV therapy continues for a minimum of 6 months after discontinuation of all anti-cancer therapy or for up to 24 months after registration, whichever comes first.

b. Arm 4: Usual Care Anti-Viral Therapy

Initiate anti-HBV therapy at the discretion of the physician. Any FDA approved anti-viral medication for treatment of HBV may be utilized. See [Section 18.5](#).

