7.4 HBV Monitoring and Adverse Liver Outcomes

During anti-cancer therapy and for 24 months from initial registration, all patients will undergo monitoring for HBV reactivation and adverse liver outcomes (see [Section 10.0](#)). Patients will have ALT and total bilirubin assessed every 4 weeks (\pm 2 weeks) for the first 24 weeks, then every 8 weeks thereafter. Per usual care, if total bilirubin > 3 mg/dL or if ALT > 5x IULN or > 200 U/L then INR will be assessed.

As part of adverse liver outcome assessment, if a hepatitis flare occurs (defined as ALT > 3 x baseline and > 100 U/L) the following labs should be ordered on the same day as the flare or within 7 days of the flare:

- direct bilirubin,
- HBV DNA,
- IgM anti-HAV, and
- either anti-HCV or HCV RNA.

- Patients on Arms 1, and 2 must have HBeAg tested. HBV test results must be reported on the **S1614** Laboratory Values Form.
- If Patients on Arms 3 and 4 become HBsAg positive and have a hepatitis flare, HBeAg testing is required. HBV test results must be reported on the **S1614** Laboratory Values Form.

Additionally, for all HBsAg+ patients, it is recommended that the treating investigator contact [name], M.D., [name], M.D., or [name] at [contact] for evaluation during the study treatment and after discontinuation of study treatment to ensure continued monitoring and to determine whether antiviral therapy should be maintained after discontinuation of study treatment.

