9.2 ARM 2 & ARM 3: Upon Indication Arms (HBsAg+ or HBsAg- Patients)

REQUIRED STUDIES	Week 0 (Registration)	Weeks from Registration (± 2 weeks unless otherwise specified)						Follow-Up after Off HBV Treatment (Every 8 Weeks Through Week 104 (24 months)	at HBV Reactivation
		4	8	12	16	20	24		
PHYSICAL									
History and Physical Exam	X								
HBV Assessment ^(H)	X	X	X	X	X	X	X	X	X
Toxicity Notation ^{(G) (H)}		X	X	X	X	X	X	X	
Review Intake Calendar ^{(G) (H)}		X	X	X	X	X	X	X	
LABORATORY									
Serum creatinine/Creatinine Clearance	X	X	X	X	X	X	X	X	
Total Bilirubin	X	X	X	X	X	X	X	X	
Direct Bilirubin ^{(A) (F)}									
ALT	X	X	X	X	X	X	X	X	
International Normalized Ratio(INR) ^(A)	X	X	X	X	X	X	X	X	
Complete Blood Count	X								
HBV DNA ^{(B) (C) (F)}	X	X	X	X	X	X	X	X	
HBsAg ^(C)	Not Indicated in Arm 2*								
IgM anti-HAV ^{(B) (C) (F)}	X	X	X	X	X	X	X	X	
anti-HCV ^{(B) (C) (F)} or HCV RNA ^{(B) (C) (F)}		X	X	X	X	X	X	X	
Anti-HBs (Arm 3) ^{(B) (C) (F)}	X	X	X	X	X	X	X	X	
HBeAg (if become HBsAg+) ^{(B) (C) (F)}	X	X	X	X	X	X	X	X	

REQUIRED STUDIES	Week 0 (Registration)	Weeks from Registration (± 2 weeks unless otherwise specified)							Follow-Up after Off HBV Treatment (Every 8 Weeks Through Week 104 (24 months)	at HBV Reactivation
		4	8	12	16	20	24			
SPECIMEN SUBMISSION ^(D)										
Serum (10 ml blood in red top tube)	X		X		X		X	X		X
Whole blood (50 ml in EDTA tubes)	X			X			X			X
TREATMENT										
Upon-Indication anti-HBV therapy ^(E)	X	X	X	X	X	X	X	X		

NOTE: Forms are found on the protocol abstract page on the SWOG website (www.swog.org). Forms submission guidelines are found in [Section 14.0](#).

NOTE: Unless indicated otherwise in the protocol, scheduled procedures and assessments (treatment administration, toxicity assessment for continuous treatment, disease assessment, specimen collection and follow-up activities) must follow the established SWOG guidelines as outlined in SWOG Best Practices, <https://www.swog.org/clinical-trials/protocol-workbench>.

FOOTNOTES for Calendar 9.2:

- (A) If total bilirubin > 3 mg/dL, or if ALT > 5x IULN or > 200 U/L, per usual care (see [Section 7.4](#)).
- (B) If hepatitis flare (defined as ALT > 3 x baseline and > 100 U/L) if patient is HBsAg-positive.
- (C) If hepatitis flare (defined as ALT > 3 x baseline and > 100 U/L) in patient with baseline HBsAg-negative.
- (D) See [Sections 15.0](#) and [Appendix 18.1](#).
- (E) See [Section 7.0](#)

(F) To be ordered the same day (or within 7 days) if hepatitis flare occurs.

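### Section 11.2 claims 81% power at a hazard ratio of 0.47 for HBV reactivation in both cohorts, but the Cohort 2 design gives no treatment mechanism for that effect

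*Combined protocol and SAP*

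**What the plan says.** Section 1.2b sets a time-to-event secondary objective for the past-infection cohort: "to compare the effect of upon indication anti-HBV therapy versus usual care on HBV reactivation". Section 11.2 carries it into the analysis for both cohorts ("The investigators will also compare HBV reactivation rates by arm within each randomized trial"). It then gives one power statement, without separating the cohorts: 222 patients, 111 per arm, at one-sided alpha 0.05 "will give 81% power to detect a hazard ratio for HBV reactivation for experimental to standard arms of 0.47". The hazards behind it are 0.223 on the standard arm and 0.105 on the experimental arm, with a competing death hazard of 0.223.

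Section 10.2c fixes when the experimental therapy begins: "On Arms 2 and 3, anti-HBV therapy is initiated only when HBV reactivation occurs". Section 7.3a says the same for Arm 3; after a hepatitis flare the site should "then obtain HBV DNA test per usual care. Start anti-HBV therapy if HBV reactivation occurs". For the comparator, Section 7.3b reads: "Initiate anti-HBV therapy at the discretion of the physician".

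Scheduled monitoring does not differ by arm. Under Section 7.4, "all patients will undergo monitoring for HBV reactivation and adverse liver outcomes". For patients who are HBsAg-negative at baseline, footnote C of calendars 9.2 (Arm 3) and 9.3 (Arm 4) puts post-baseline HBV DNA testing under the same condition: "If hepatitis flare (defined as ALT > 3 x baseline and > 100 U/L) in patient with baseline HBsAg-negative".

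**The concern.** A therapy that begins when an event occurs cannot lower the hazard of the first such event. In Cohort 1 the difficulty does not arise, because Section 7.2a starts Arm 1 therapy before anti-cancer therapy or within 42 days of its first dose, so a hazard ratio below 1 for Arm 1 against Arm 2 is plausible. In Cohort 2 the experimental arm is itself the upon-indication arm, and its trigger is the endpoint.

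What is at stake is how the result is read. Section 11.2 calls reactivation the main secondary objective of each cohort. If the Cohort 2 comparison is null and the plan describes it as 81% powered, a reader could conclude that upon-indication therapy was fairly tested and failed. Its possible benefit lies after reactivation, in preventing liver failure or liver-related death, and the primary endpoint measures that.

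**Working it through.** **Inputs.** From Section 11.2: reactivation hazards 0.223 and 0.105 per year, hazard ratio 0.47, death hazard 0.223, one-sided alpha 0.05, 222 patients. From Section 11.1: 200 patients before the allowance for 10% dropout. From Section 7.8: follow-up to 24 months. Equal allocation and exponential times are taken throughout.

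**Formulas.** With reactivation hazard λ, death hazard μ and follow-up T, the probability of an observed reactivation is λ/(λ+μ) × (1 − exp(−(λ+μ)T)). With D expected events, Schoenfeld power is Φ(√D/2 × |ln HR| − 1.645).

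**1. The plan's own figure.**
- Standard arm: 0.5 × (1 − exp(−0.892)) = 0.295.
- Experimental arm: 0.105/0.328 × (1 − exp(−0.656)) = 0.154.
- 100 evaluable per arm: D = 29.5 + 15.4 = 44.9. Power = Φ(6.70/2 × 0.755 − 1.645) = Φ(0.885) = 81.2%.
- 111 per arm: D = 49.8, and Schoenfeld power is 84.6%. Freedman's formula gives 81.6%.

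The stated 81% is therefore reproduced, with 24 months of follow-up, either by Schoenfeld at 200 or by Freedman at 222.

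**2. Does the effect apply to Cohort 2?**

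| Feature before first reactivation | Arm 3 | Arm 4 | Section |
|---|---|---|---|
| Antiviral therapy | None under protocol until the 10.2a event | Physician's discretion | 7.3, 10.2c |
| ALT and bilirubin schedule | Every 4 weeks to week 24, then every 8 weeks | Same | 7.4 |
| HBV DNA test after baseline | On hepatitis flare | Same | 9.2 and 9.3, footnote C |
| Central testing of stored serum | Retrospective | Same | 18.1 |

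The only difference in treatment before reactivation is that Arm 4 physicians may treat early. That would lower the Arm 4 hazard and push the Arm 3 to Arm 4 hazard ratio above 1. Section 11.3 already provides for monitoring the Arm 4 treatment rate. No row gives a treatment mechanism for a ratio below 1.

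**3. The Cohort 2 comparison at a hazard ratio of 1.** With 100 per arm, D = 2 × 100 × 0.295 = 59.0. The chance of a significant result favouring Arm 3 is Φ(0 − 1.645) = 5.0%, that is, alpha.

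**4. What Cohort 2 can estimate.** Assumptions: hazard ratio 1, death hazard 0.223, 24 months of follow-up for the hazard ratio, and the one-year difference in cumulative incidence after competing death. Half-width = 1.96 × √(2p(1−p)/n). Hazard ratio interval = exp(±1.96 × 2/√D).

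| Reactivation hazard | Evaluable per arm | One-year cumulative incidence p | Half-width | Events D | Hazard ratio interval |
|---|---|---|---|---|---|
| 0.223 | 100 | 0.5 × (1 − exp(−0.446)) = 18.0% | ±10.6 points | 59.0 | 0.60 to 1.67 |
| 0.223 | 111 | 18.0% | ±10.1 points | 65.5 | 0.62 to 1.62 |
| 0.105 | 100 | 0.320 × (1 − exp(−0.328)) = 9.0% | ±7.9 points | 30.8 | 0.49 to 2.03 |

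Hazard 0.105 corresponds to 10% at one year without competing death. Ten per cent is the low end of the 10-20% range that Section 2.1 gives for past infection.

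**The case against.** The strongest reply is that a power statement is conditional. It says what the trial could detect if the hazard ratio were 0.47 and does not forecast that Arm 3 will reach it. The Cox model stays valid at a ratio of 1, no sample size or stopping rule depends on the sentence, and the efficacy question in Cohort 2 belongs to the liver-outcome endpoint. Section 11.2 already puts estimation of incidence first, and the arm comparison comes after it. All of this stands, and it confines the point to wording. It does not justify attaching a superiority power claim to an effect for which the Cohort 2 design has no treatment mechanism. The feared misreading is a risk in later reporting; the plan does not itself propose that reading.

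A reader might go further and infer that the observed Cohort 2 hazard ratio must be 1, or can exceed 1 only through early treatment in Arm 4. The documents do not support that. The arms are open, unscheduled local HBV DNA tests are not excluded, and Section 11.2 does not say whether local results or retrospective central testing feed the analysis. Unequal local testing could move the observed ratio in either direction. That would be ascertainment and not a treatment effect, so it does not rescue 0.47.

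A reader might also infer that the 81% is miscalculated, or that Cohort 2 as a whole is undermined. Neither follows: the figure reproduces, and therapy begun at reactivation can still prevent later liver failure.

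**Conclusion.** The concern holds for Cohort 2 reactivation and no further. The documents give no treatment mechanism for an Arm 3 to Arm 4 hazard ratio below 1, so the 81% power statement should not be applied there. If the true ratio is 1, the probability of a significant one-sided result favouring Arm 3 is 5%. If Arm 4 physicians treat before reactivation it is lower, by an amount the documents give no basis to calculate.

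The conclusion rests on the Section 10.2c definition of upon-indication therapy and on the equal monitoring schedules. The 5% does not depend on the assumed event rate; the precision figures do.

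Section 1.2 does not define the combined endpoint of adverse liver outcome and reactivation as the first of either event. If that is what is meant, the same reasoning applies to the reactivations in it, and Section 11.2 gives no power figure for it. Nothing is claimed here about hepatitis flare. The primary endpoint, the sample size, Cohort 1 and the reactivation incidence estimate are unaffected.

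**What to change.** In Section 11.2, limit the sentence with hazard ratio 0.47 and 81% power to Cohort 1. For Cohort 2, keep the planned cumulative incidence by arm and the Cox model. State in Sections 1.2b and 11.2 that the between-arm reactivation result is reported with a two-sided 95% confidence interval, as estimation and not as a powered test of the efficacy of Arm 3 therapy. Apply the same sentence to the combined endpoint if it is defined as the first of either event.

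If expected precision is quoted, state its assumptions beside it: hazard ratio 1, death hazard 0.223, 24 months of follow-up, the number evaluable per arm, and the cumulative incidence after competing death. Give both the 18.0% and the 9.0% cases from the table above.

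The cost is a few sentences in two sections and the loss of the 81% claim for Cohort 2 reactivation. Data collection, sample size, the primary analysis and clinical management do not change.
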